SURGERY WITH OR WITHOUT STEROTACTIC BODY RADIOTHERAPY

A Prospective Randomized Phase II Study of Surgery with or without Adjuvant Stereotactic Body Radiotherapy (SBRT) in Patients with Previously-Irradiated Head and Neck Cancer

(Version Dated 2020-04-29)

Principal Investigator:

[name], PhD
UPMC Cancer Center
Mary Hillman Jennings Radiation Oncology Center
[name]
[name]
[name]
[contact]
Ph: [contact]
[contact]

Study Co-Investigators:

Radiation Oncology

[name] ([contact])
[name], PhD ([contact])
[name] ([contact])

Hematology Oncology

[name] [name] ([contact])

Otolaryngology

[name] [name] ([contact])
[name] ([contact])
[name] ([contact])
[name] ([contact])

Biostatistics

[name] ([contact])

TABLE OF CONTENTS

PROTOCOL SUMMARY	3
1.0 BACKGROUND	5
2.0 OBJECTIVES	7
3.0 INVESTIGATIONAL PLAN.....	8
4.0 SUBJECT SELECTION AND ELIGIBILITY.....	11
5.0 TREATMENT EVALUATION, ADMINISTRATION, AND MODIFICATION...	13
6.0 STATISTICAL CONSIDERATIONS.....	14
7.0 DATA SAFETY AND MONITORING.....	16
8.0 REFERENCES	17

PROTOCOL SUMMARY

Title

A Prospective Randomized Phase II Study of Surgery with or without Adjuvant Stereotactic Body Radiotherapy (SBRT) in Patients with Previously-Irradiated Head and Neck Cancer

Objectives

The *primary* objective of this study is to compare the 1-year local control in patients with operable, recurrent previously-irradiated squamous cell head-and-neck cancers with or without adjuvant SBRT.

The *secondary* objectives of this study are:

1. To determine the locoregional progression-free survival (PFS), distant PFS, overall PFS (local + regional + distant), and overall survival (OS).
2. To evaluate the acute and late toxicities of adjuvant SBRT in the re-irradiation setting following salvage surgery.
3. To determine prognostic factors that may predict the likelihood of local failure, regional failure, or OS in this cohort to guide future management.
4. To compare the impact of adjuvant SBRT versus a wait-and-see approach on patient reported quality of life (PR-QoL).
5. To compare surgical versus SBRT-induced immunological serum markers in relation to local control.

Patient population

In order to be eligible for this study, patients must have a pathologically proven recurrent or second-primary head-and-neck cancer with no evidence of distant metastases. Patients must be at least 18 years of age and able to give informed consent. They must have a Karnofsky Performance Status ≥ 60 .

Number of patients

42

Study design and methodology

This is a prospective, double-arm phase II study. The treatment schema detail is in Section 6.3.

Treatment administered

Patients will or will not receive adjuvant Stereotactic Body Radiotherapy (SBRT) at various levels depending upon tumor volume. Subsequent evaluations will measure the efficacy of the adjuvant SBRT.

Efficacy data collected

The following evaluations will be performed to assess the efficacy of preoperative stereotactic radiation therapy:

- Objective local control rate measuring tumor volume
- Health Related Quality of Life assessment using the University of Washington Quality-of-Life-Revised (UW-Qol-R)

Safety data collected

The following evaluations will be conducted to assess the safety of radiosurgery:

- Recording of all toxicity data per NCI CTCAE version 4.0

1.0 BACKGROUND

1.1 Salvage Surgery for Recurrent Head-and-Neck Cancers

Recurrent and second-primary head-and-neck cancers (rHNC) in a previously-irradiated field represent a therapeutic challenge (1). Even with adjuvant therapy, rHNC occurs in $\geq 20\text{-}30\%$ of high-risk postoperative patients and $\geq 30\%$ of patients treated with definitive chemoradiotherapy (2-3). While there are no randomized data to test the benefits of salvage surgery after prior irradiation, for patients who can have surgical resection, based on available data, surgical resection represents the currently accepted standard of care (4-5). However, even patients with resectable rHNC are at high-risk for subsequent failure (67% overall failure rates). In patients with close or positive surgical margins following salvage surgery, recurrence rates of nearly 100% have been reported (6). To improve tumor control in this setting adjuvant re-irradiation techniques along with chemotherapy has been used with mixed but limited success (7-10).

1.2 Adjuvant Re-Irradiation

The only phase III experience evaluating adjuvant therapy after surgical salvage is from the Institute Gustave-Roussy (7). In this phase III study, 130 previously-irradiated rHNC patients were randomized following salvage surgery to chemotherapy + re-irradiation (CT/Re-RT) versus observation. Chemotherapy consisted of six cycles of hydroxyurea and continuous infusion 5-FU, while adjuvant re-irradiation was delivered to a total dose of 60 Gy in a split-course fashion (the contemporaneous RTOG standard). Disease-free survival (DFS), but not overall survival (OS), was improved with the addition of adjuvant CT/Re-RT (the study was not powered for OS). However, this treatment was not without toxicity. Grade 3 or 4 mucositis was seen in 28% of patients and 39% of patients had grade 3 or 4 late toxicity versus only 10% of patients in the observation arm. This is the only level I evidence for adjuvant therapy in re-irradiation setting. Thus the data supports the role of re-irradiation in improving local control albeit with the expense of significant toxicity.

1.3 Stereotactic Body Radiotherapy

Stereotactic body radiotherapy (SBRT), is a treatment technique that incorporates advances in radiation planning and delivery to provide highly conformal doses of radiation with a steep-dose gradient to surrounding critical organs-at-risk. Since 2001, researchers at the University of Pittsburgh Cancer Institute have been pioneers in the use of frameless extracranial SBRT for a variety of benign and malignant lesions. The advantages of SBRT in the setting of re-treatment of high-risk patients with head and neck carcinomas are a highly conformal treatment volume that affords a small number of fractions, decreased overall treatment time, and radiobiological advantages (where acute responding tissue is better spared with higher doses per fraction/lower overall dose) minimizing acute toxicity.

1.4 Experiences with SBRT at the University of Pittsburgh

Stereotactic body radiotherapy (SBRT) has emerged as a promising treatment option in patients with unresectable rHNC. Initial phase I dose-escalation study from the University of Pittsburgh Cancer Institute established the safety of SBRT up to 44 Gy in 5 fractions (11). Numerous subsequent international single-institution studies have confirmed the primary benefits of SBRT relative to conventional re-irradiation \pm chemotherapy for unresectable rHNC: decreased toxicity with comparable tumor control/survival (12-17).

Further studies from the University of Pittsburgh Cancer Institute have established a dose volume response model and shown similar outcomes for non-squamous versus squamous histologies (18-19). Moreover, longitudinal prospective evaluations of patient-reported quality of life (PR-QoL) have shown that improved tumor control associated with SBRT reirradiation ameliorates decreased PR-QoL resulting from rSCCHN which transcended all measured domains in a validated PR-QoL assessment tool. This improvement was independent of age, use of cetuximab, tumor volume, and interval since prior irradiation (20). Finally, recent prospective data has suggested that the addition of cetuximab to SBRT may improve tumor control without significant increases in re-irradiation toxicity for unresectable rHNC (21-22). While there is growing evidence for SBRT in unresectable rHNC, there is limited data in the adjuvant setting (23). We recently reported our experience using SBRT following salvage surgery for patients with compromised/positive surgical margins and extra-nodal extension at high-risk for recurrence (24). Based on these results, SBRT may improve tumor control relative to salvage surgery alone and reduce toxicity relative to conventional adjuvant radiotherapy ± chemotherapy in rHNC (see Table 1). We seek to confirm these retrospective observations with the prospective trial evaluating SBRT to observation post-surgery.

2.0 OBJECTIVES

Primary

- 2.1 To compare the 1-year local control in patients with operable, recurrent previously-irradiated squamous cell head-and-neck cancers with or without adjuvant SBRT.

Secondary

- 2.2 To determine the locoregional progression-free survival (PFS) distant PFS, overall PFS (local + regional + distant), and overall survival (OS).
- 2.3 To evaluate the acute and late toxicities of adjuvant SBRT in the re-irradiation setting following salvage surgery.
- 2.4 To determine prognostic factors that may predict the likelihood of local failure, regional failure, or OS in this cohort to guide future management.
- 2.5 To compare the impact of adjuvant SBRT versus a wait-and-see approach on patient reported quality of life (PR-QoL).

3.0 INVESTIGATIONAL PLAN

3.1 Overall design and plan of the study

Detailed visit-by-visit study procedures and a study flow chart are provided in Section 6.3. Prior to enrollment, all subjects will be evaluated with medical records to confirm patient received diagnosis of recurrent or second-primary head-and-neck squamous cell carcinomas. Additionally, these records will confirm the patient had had macroscopic complete (R0/R1) salvage surgery and previous radiation. Patients will receive a Stereotactic Body Radiotherapy and then followed periodically for up until 2 years.

3.2 Screening procedures

- Medical history (including review of pathology and laboratory values) and physical examination
- Pathologic confirmation of diagnosis and disease status/staging with biopsy to rule out metastatic disease (if necessary)
- Baseline laboratory assessment, including CBC and blood chemistry
- Urine or blood β -HCG within 14 days prior to study start for females who are not at least one year post-menopausal or who have not undergone a surgical sterilization procedure
- CT or PET-CT of the neck and chest
- Baseline Quality of Life Assessment

3.3 Personnel performing the procedures

All procedures will be performed by appropriate certified medical personnel, including, but not limited to physicians, nurses, technologists and research staff.

3.4 Location and duration of procedures

All study visits will take place on an outpatient basis in the UPMC Shadyside Radiation Oncology Department. However, it is possible that a subject may be an inpatient at the time of diagnosis. All procedures will be performed by appropriate certified medical personnel.

3.5 Timeline of study procedures

Once eligible by screening and enrolled in study, patients will be randomized into one of two arms. One arm will receive SBRT treatment for 1 – 2 weeks. The second arm will receive no SBRT and will continue with standard of care treatment. Patients will be followed for 8-12 weeks after treatment and every 3-6 months for up to 24 additional months. Extended long-term follow-up will occur as clinically indicated until death.

3.6 Research Activities

3.6.1 Pretreatment Evaluation

The following tests/procedures will be performed within 3 months prior to registration unless otherwise specified:

- Medical history and physical examination
- Pathologic confirmation of diagnosis and disease status/staging with biopsy to rule out metastatic disease if necessary
- Baseline laboratory assessment, including CBC and blood chemistry

- Urine or blood β -HCG within 14 days prior to study start for females who are not at least one year post-menopausal or who have not undergone a surgical sterilization procedure
- CT (computed tomography) scan or FDG-PET-CT (^{18}F -fluorodeoxyglucose positron emission tomography/computed tomography) of the neck and chest
- Baseline Quality of Life Assessment (University of Washington – Quality of Life – Revised (UW-QoL-R)

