6.2 Sample size and accrual rate

Forty (40) patients will be screened for each arm of the trial so that 21 subjects will be cleared to participate in research procedures in each arm of the trial.

The following assumptions are used in determining the sample size for this study:

Primary endpoint: local progression-free survival (LPFS)

One-sided type I error rate: 0.10

Statistical power: 90%

One-year LPFS for surgery alone: 20%

One-year LPFS for surgery + SBRT: 52%

Randomization: 1:1

2-year accrual period and one year follow-up following closure of accrual

5% lost to follow-up in each arm

To have 90% power to detect the above 32% difference in one-year LPFS, using a onesided log-rank test with a 0.1 level of significance, 21 patients are required in each arm.

The randomization of subjects to one of the two treatment arms will be in a 1:1 ratio. The UPCI Biostatistics Facility has a randomizer, an intranet application for randomly assigning patients to different treatments, which will be used for the randomization in this trial.

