6.4 Analysis of primary and secondary endpoints

Survival endpoints will be estimated by the Kaplan-Meier method and the corresponding median survival times (with 95% confidence interval) reported. The one-year LPFS will also be estimated along with its 95% confidence interval. Survival will be compared between the two arms with the one-sided log-rank test. Effect of treatment and other variables (e.g., baseline characteristics, biomarkers etc) on survival will be explored with Cox regression models.

For the quality of life (QoL) data analysis, each item of the UW-QoL-R will be individually assessed. The mean and standard deviation of the observed data will be summarized at each collection time and plotted against time, from baseline through the end of patient follow-up. Generalized linear models (such as cumulative logit models) for repeated measures will be used to explore if there are significant changes in PR-QOL over time.

Using NCI Common Terminology Criteria for Adverse Events (CTCAE v4.0), the number of patients experiencing adverse events over their course of treatment will be characterized by type of adverse event and grade, by the time of onset in relation to the first day of therapy, and whether the event is clinically significant. Attribution of adverse events to treatment (unrelated, unlikely, possibly, probably, or definitely) will also be summarized for any serious adverse events (SAEs), CTCAE grade 3 or higher. The percentage of patients experiencing SAEs that are considered to be treatment-related (probable or definite) will be determined. The percentages of patients experiencing the acute/late toxicities associated with SBRT will also be estimated along with their exact 95% confidence intervals.

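### The quality-of-life model in section 6.4 names no arm contrast and no use of the baseline UW-QoL-R score, so objective 2.5 has no specified analysis and an available gain in efficiency is left unclaimed

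*Combined protocol and SAP*

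**What the plan says.** Sections 3.2 and 3.6.1 list a pretreatment questionnaire among the screening tests: "Baseline Quality of Life Assessment (University of Washington – Quality of Life – Revised (UW-QoL-R". The general window in 3.6.1 is three months before registration. Section 3.6.4 repeats the assessment at follow-up in both arms.

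Objective 2.5, restated in 6.1, is comparative: "To compare the impact of adjuvant SBRT versus a wait-and-see approach on patient reported quality of life (PR-QoL".

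The only analysis text for these data is one paragraph of section 6.4. Each item is handled separately. Means and standard deviations are tabulated and plotted at each collection time, starting at baseline. Generalized linear models, with cumulative logit models as the example, "for repeated measures will be used to explore if there are significant changes in PR-QOL over time". The paragraph names no treatment term, arm-by-time term, target visit or baseline covariate. It does not say whether the baseline record enters the model as an outcome. Baseline characteristics appear as possible covariates in 6.4 only for the Cox survival models.

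On allocation, 6.2 gives "Randomization: 1:1". Neither 3.6.2 nor 6.2 describes stratification.

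**The concern.** The objective asks whether SBRT changes quality of life relative to observation. The model text asks whether quality of life changes over time. To meet the objective, someone must choose a between-arm contrast, and the text leaves open whether it is a follow-up difference, a difference in change from baseline, or a baseline-adjusted difference. In a small trial these can give visibly different answers, and the choice could be made after the data are seen.

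Two things are at stake. Chance differences between arms at baseline will be sizeable with 42 patients, and the contrasts treat them differently. The baseline score is also collected on everyone and is probably the best available predictor of the later score, so not using it gives up efficiency at no saving. Quality of life is one of the places where the burden of SBRT on the patient would show.

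**Working it through.** **Plan's own figure.** The documents give no SD, effect size, alpha or power for quality of life, so the only design figure to reproduce is 21 per arm for LPFS. Inputs from 6.2: "One-sided type I error rate: 0.10"; "Statistical power: 90" (per cent); "One-year LPFS for surgery alone: 20" and "One-year LPFS for surgery + SBRT: 52" (per cent); two years' accrual, one further year of follow-up, 5% loss.

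- Hazard ratio under exponential survival: ln(0.52)/ln(0.20) = 0.406.
- Schoenfeld events: 4 × (1.2816 + 1.2816)² / [ln(0.406)]² = 32.4.
- Event probabilities: 0.940 (surgery alone) and 0.710 (SBRT), mean 0.825.
- Patients: 32.4/0.825 = 39.3; divided by 0.95, 41.3; per arm 20.7, rounded up to 21.

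The figure reproduces, and n = 21 per arm is used below.

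**Chance baseline imbalance, in SD units.** Standard error = √(2/21) = 0.309. The 95% range is ±1.96 × 0.309 = ±0.60. The probability of a gap above 0.3 SD in either direction is 33%; above 0.5 SD, 11%.

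**What each contrast does with an imbalance D.** Assume equal SDs at both times and correlation r.

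- Follow-up only: expected shift r × D.
- Change from baseline: expected shift rD − D = −(1 − r)D.
- Conditional on baseline: no expected shift.

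For D at the edge of its 95% range (0.60 SD), the follow-up contrast shifts by 0.18, 0.30 and 0.42 SD at r = 0.3, 0.5 and 0.7. The change contrast shifts the opposite way by 0.42, 0.30 and 0.18 SD.

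**Efficiency at one visit, linear contrast, all 21 per arm observed.** Variance relative to follow-up only is 1 − r² when adjusted and 2(1 − r) for change. The values of r are assumptions.

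| r | SE, follow-up only | SE, change | SE, adjusted | Adjusted variance vs follow-up only |
|---|---|---|---|---|
| 0.3 | 0.309 | 0.365 | 0.294 | −9% |
| 0.5 | 0.309 | 0.309 | 0.267 | −25% |
| 0.7 | 0.309 | 0.239 | 0.220 | −49% |

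An unadjusted trial would need 42/(1 − r²) patients to match: about 46, 56 and 82. At an assumed two-sided 0.05, power for an assumed difference of 0.8 SD is 74% unadjusted and 78%, 85% and 95% adjusted.

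**Several visits.** In a simulation with baseline plus three follow-ups, equal correlations of 0.5 and 21 per arm, the standard error of the mean follow-up contrast was 0.252 for follow-up only, 0.249 for change and 0.201 adjusted.

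**Cumulative logit model.** The formulas above do not carry over to odds-ratio intervals. In a simulation with 21 per arm, five ordered categories (assumed), a latent effect of 0.8 SD and one visit, adding baseline widened the interval for the log odds ratio by about 3%, 7% and 15% at r = 0.3, 0.5 and 0.7. Power nevertheless rose, from about 74% to 77%, 71% to 79% and 72% to 91%, because the conditional log odds ratio grows more than its standard error.

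**The case against.** The strongest reply is that the plan is silent rather than wrong. A reader might infer from 6.4 that the model treats baseline as just another outcome time, but the words about starting at baseline belong to the summary and plot; the model sentence does not mention baseline. Nor would baseline as an outcome be a defect in itself: with a common baseline mean across arms, such a model is about as precise as covariate adjustment. Both replies stand.

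A reader might also infer that an unadjusted comparison takes on the whole baseline imbalance. It does not: a follow-up contrast carries the fraction r, and a change contrast subtracts the imbalance and overshoots.

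A third tempting reading is that adjustment would narrow the planned intervals by the percentages a linear model implies. The plan's example is a cumulative logit model, where the odds-ratio interval does not narrow and the adjusted odds ratio is conditional on baseline, a different quantity.

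Finally, r is unknown. The three-month window may put some baselines before salvage surgery, which could lower r. At r = 0.2 the variance falls by only 1 − 0.96 = 4%. The endpoint is secondary, explored item by item and unpowered. All of this limits the size of the gain. It does not supply the missing arm contrast, and the silence itself leaves the analysis open to choice after the data are seen.

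**Conclusion.** The concern holds as a gap in specification. A comparative objective has no stated comparative analysis, and a baseline score already being collected has no stated role in the model. Choosing follow-up only or change from baseline would give up efficiency to adjustment for any r strictly between 0 and 1.

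The variance reductions of 9% to 49% relative to follow-up only rest on an assumed r of 0.3 to 0.7, equal SDs, a linear contrast at one visit, and all 21 per arm observed. The last assumption is optimistic for later visits: LPFS counts deaths, and its planned one-year values are 20% and 52%, so fewer patients may be available and imbalance among them may be larger. With a cumulative logit model the benefit should be stated as power.

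The documents do not support saying that the plan mis-models baseline, or that the randomized comparison is biased on average. The LPFS analysis and its sample size are unaffected.

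**What to change.** In section 6.4:

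1. Add arm and arm-by-time terms to the quality-of-life model and name the visit at which the arm difference will be read.
2. Enter the baseline score of the same item (for a cumulative logit model, its baseline category) as a covariate, with post-baseline records as the outcomes. Alternatively, keep baseline as an outcome and constrain the arms to one common baseline mean.
3. State that the arm difference for objective 2.5 comes from this model and, if it is a cumulative logit model, that the odds ratio is conditional on baseline.

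This costs a few sentences and needs no new data or patients. If some baseline forms may be missing, the common-mean version keeps those patients in the analysis.

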3.6.3 Treatment

Steriotactic Body Radiotherapy (SBRT) will be performed on 1 of the treatment arms. Group 1 will receive SBRT for 1-2 weeks.

3.6.3.1 Tumor Volume

Tumor volumes $<25\text{cc}$ will receive 40Gy (5 fractions of 8Gy per fraction). Tumor volumes $\geq 25\text{cc}$ will receive 44-50Gy (5 fractions of 8.8 – 10 Gy per fraction). Ideally, all tumor volumes $\geq 25\text{cc}$ will receive 50Gy over 5 fractions; however, at the discretion of the treating radiation oncologist based on tumor bed volume, prior radiation dose, and proximity to critical organs, the dose can be reduced to 44 Gy over 5 fractions.

3.6.3.2 Randomized Arm

Patients randomized to the adjuvant SBRT arm will receive 40-50Gy in 5 fractions on non-consecutive days in 1-2 weeks on an outpatient basis. SBRT should be completed at a minimum of 4-weeks following salvage surgery, with a maximum of 12-weeks. CTV (clinical target volume) will represent the tumor bed/high-risk region as defined by head and neck surgeon and radiation oncologist. A maximum of 5mm expansion from CTV to PTV (planning target volume) shall be applied

Treatment Volumes $< 25\text{cc}$ will receive 40Gy (5 fractions of 8 Gy per fraction)
 Treatment Volumes $\geq 25\text{cc}$ will receive 44-50Gy over 5 fractions (5 fractions of 8.8Gy per fraction). Ideally, all tumors volumes $\geq 25\text{cc}$ will receive 50Gy over 5 fractions; however, at the discretion of the treating radiation oncologist based on tumor volume, prior radiation dose and proximity to critical organs, the dose can be reduced to 44Gy over 5 fractions as outlined in prior SBRT protocols.

